#### 13.4. Reporting Adverse Events

The Investigator will notify the Sponsor of an adverse event by e-mail, facsimile, or telephone as soon as possible and no later than 24 hours from discovery for any serious /significant adverse events, and 2 days from discovery for any non-significant adverse event. In addition, a written report will be submitted by the Principal Investigator to the IEC/IRB according to their requirements (section 13.4.2). The report will comment whether the adverse event was considered to be related to the test article, study treatment or study procedures.

#### 13.4.1. Reporting Adverse Events to Sponsor

#### Serious/Significant Adverse Events

The Investigator will inform the sponsor of all serious/significant adverse events occurring during the study period as soon as possible by e-mail or telephone, but no later than 24 hours following discovery of the event. The Investigator is obligated to pursue and obtain information requested by the Sponsor in addition to that information reported on the eCRF. All subjects experiencing a serious/significant adverse event must be followed up and all outcomes must be reported.

When medically necessary, the Investigator may break the randomization code to determine the identity of the treatment that the subject received. The Sponsor and study monitor should be notified prior to unmasking the test articles.

In the event of a serious/significant adverse event, the Investigator must:

- Notify the Sponsor immediately.
- Obtain and maintain in the subject's records all pertinent medical information and medical judgment for colleagues who assisted in the treatment and follow-up of the subject.
- Provide the Sponsor with a complete case history which includes a statement as to whether the event was or was not related to the use of the test article.
- Notify the IEC/IRB as required by the IEC/IRB reporting procedure according to national regulations.

#### **Non-Serious Adverse Events**

All non-serious adverse events, including non-serious adverse device effects, will be reported to the sponsor by the Investigator no later than 2 days from discovery.

#### 13.4.2. Reporting Adverse Events to the Responsible IEC/IRB and Health Authorities

Adverse events that meet the IEC/IRB requirements for reporting must be reported within the IEC/IRB's written guidelines. Each clinical site will refer to and follow any guidelines set forth by their Approving IEC/IRB. Each clinical site will refer to and follow any guidelines set forth by their local governing Health Authorities.

The Sponsor will report applicable Adverse Events to the local health authorities according to the written guidelines, including reporting timelines.

#### 13.5. Event of Special Interest

None

#### 13.6. Reporting of Pregnancy

Subjects reporting pregnancy (by self-report) during the study will be discontinued after the event is recorded as an Adverse Event. Once discontinued, pregnant participants and their fetuses will not be monitored for study related purposes. Pregnant participants are not discontinued from artificial tear solution related studies for safety concerns, but due to general concerns relating to pregnancy and solution use. Specifically, pregnant women are

discontinued due to fluctuations in refractive error and/or visual acuity that occur secondary to systemic hormonal changes, and not due to unforeseen health risks to the mother or fetus.

# 14. STATISTICAL METHODS

#### 14.1. General Considerations

A separate Statistical Analysis Plan (SAP) will be created. Statistical Analysis will be undertaken by the sponsor or under the authority of the sponsor. A general description of the statistical methods to be implemented in this clinical trial is outlined below. Further details will be included in the SAP.

All data summaries and statistical analyses will be performed using the SAS software Version 9.4 or higher. Throughout the analysis of data, the results for each subject/eye will be used when available for summarization and statistical analysis. Unscheduled visits will be summarized separately and will be excluded from any efficacy analyses. However, unscheduled visits will be included in any analysis that may be conducted on safety endpoints.

Summary tables (descriptive statistics and/or frequency tables) will be provided for all baseline variables, efficacy variables and safety variables as appropriate. Continuous variables will be summarized with descriptive statistics (n, mean, standard deviation (SD), median, minimum, and maximum). Frequency count and percentage of subjects or eyes within each category will be provided for categorical data.

#### 14.2. Sample Size Justification

This study was designed and powered to demonstrate non-inferiority of the Preservative-free investigational lubricating eye drops in a Novelia® eyedropper compared to the Blink® Tears eye drops with respect to monocular distance (4m) HLLC logMAR at 10-minutes after the instillation, with a 0.05 logMAR non-inferiority margin. If the investigational lubricating eye drops perform on average worse than 0.05 logMAR the visual acuity may be considered clinically unacceptable. The sample size was calculated for the primary endpoint to achieve a minimum power of 90% using a 2-sided type I error of  $\alpha = 0.05$  based on historical data from

was a 2x2 crossover study with two eye drops; the control eye drop being the same as the current study Table 9 below presents the descriptive statistics of monocular logMAR visual acuity observed at 10 minutes after instillation in the same as the current study.

Table 9: Descriptive Summary	of Monocular LogMAR	Visual Acuity from	- Per Protoco

- Per Protocol Population

Endpoint	Investigational eye drops	Blink ® Tears eye drops
Number of eyes	62	62
Mean (SD)	0.09 (0.095)	0.09 (0.087)

SD=Standard Deviation

Monocular distance (4 m) High Luminance, Low Contrast (HLLC) logMAR visual acuity

The sample size estimate for monocular distance logMAR visual acuity was calculated using a linear mixed model-based power analysis method. The model included eye drop as fixed effects. An unstructured (UN) covariance matrix was used to model the residual errors between measurements within the same subject and eye across study periods. For a more conservative assessment compared to the average observed historical studies delta shown above, it was assumed that the visual performance of the investigational eye drop is 0.025 logMAR lower compared to the control eye drop. Sample size estimation was carried out using an approximation of the power of an F-test derived from the noncentrality parameter calculated from the observed F statistic of the linear mixed model. The SAS procedure PROC GLIMMIX (SAS software Version 9.4) was used to perform the calculation. Below is the variance-covariance matrix used in the sample size calculation for monocular logMAR visual acuity.

Subject intercept: 0.003322

The UN covariance matrix:  $\begin{bmatrix} 0.005117 & 0.003170 \\ 0.003170 & 0.005213 \end{bmatrix}$ 

[figure not shown]

Table 10 summarizes the required number of subjects for the primary endpoint to achieve a minimum of 90% statistical power with a 2-sided type I error of 0.05.

Table 1	0: Power	for the	Primary	Endpoint
---------	----------	---------	---------	----------

Endpoint	Effect Size (Test- Control)	Margin of Non- inferiority	Sample Size	Power
Monocular logMAR VA	0.025	0.05	38	91%

As indicated in Table 10 above, the sample size was chosen for this in order to achieve a statistical power of at least 90% for the primary endpoint. The plan is to enroll approximately 45 subjects with a target of at least 38 to complete the study, assuming a 15% drop-out rate.

## 14.3. Analysis Populations

#### Safety Population:

All subjects who are administered any test article excluding subjects who drop out prior to administering any test article. Subjects will be analyzed as per treatment received.

#### **Per-Protocol Population:**

All subjects who successfully complete the study and do not substantially deviate from the protocol (i.e. have major protocol deviations) as determined by the trial cohort review committee prior to database hard lock. Justification for the exclusion of subjects with major protocol deviations from the per-protocol population set will be documented in a memo to file.

#### Intention-to-Treat (ITT) Population:

Intention-to-treat population will include all randomized subjects. Subjects will be analyzed as per planned randomized treatment.

## 14.4. Level of Statistical Significance

All planned analysis for this study will be conducted with an overall type I error rate of 5%.

## 14.5. Primary Analysis

The non-inferiority of the Preservative-free investigational lubricating eye drops in a Novelia® eyedropper compared to Blink® Tears eye drops with respect to monocular distance (4 m) High Luminance, Low Contrast (HLLC) logMAR visual acuity will be assessed on Per-Protocol (PP) population. As this is a single-visit study, the number of major protocol deviations for the evaluation of the primary endpoint is expected to be very small. The sample size was calculated conservatively in both the treatment effect size and assumed drop-out rate. Hence, the PP and ITT populations are expected to be similar. A sensitivity analysis for the primary hypothesis will be performed on intention-to-treat (ITT) population to assess the robustness the conclusions made from the primary analysis.

Monocular distance (4 m) High Luminance, Low Contrast (HLLC) logMAR visual acuity will be analyzed using a linear mixed model to compare the Preservative-free investigational lubricating eye drops in a Novelia® eyedropper compared to Blink® Tears eye drops at 10-minute after instillation. The model will include eye drops type, eye drops sequence, and period as fixed effects. Other subject characteristics such as age, gender and race will be included as fixed covariates when appropriate. Site and subject will be included in the model as random effects (G-side). The covariance of residuals between measurements on the same eye across periods within the same subject (R-side) will be modeled using Unstructured (UN) covariance structure. If the model does not converge, then other covariance structures, such as compound Symmetry (CS) covariance structure, will be considered. The Kenward and Roger method (Kenward & Roger, 1997) will be used for the denominator degree of freedom^13.

Hypothesis Testing

The null and alternative hypotheses for testing non-inferiority of the Preservative-free investigational lubricating eye drops compared to Blink® Tears eye drops with respect to monocular logMAR visual acuity are as follows:

$$H_0: \mu_T - \mu_C \ge 0.05 \\ H_A: \mu_T - \mu_C < 0.05$$

Where,  $\mu_T$  represents the mean logMAR score for the Preservative-free investigational lubricating eye drops, and  $\mu_C$  represents the mean logMAR score for the Blink® Tears eye drops. Non-inferiority will be declared if the upper bound of the 2-sided 95% confidence interval of the difference (the Preservative-free investigational lubricating eye drops – Blink® Tears eye drops) is less than the non-inferiority margin of 0.05 logMAR.

The primary hypothesis must be met for the study to be successful.

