### CHANGE HISTORY

Version	Originator	Description of Change(s) and Section Number(s) Affected	Justification for Change	Date
1.0		Original Protocol	N/A	13 March 2023
2.0		
 
Updated list of signatories
 
Section 7.2: Corrected Distance Low Contrast chart luminance acceptable range in study procedure step 1.16 from 181- 202cd/m^2 to 181-208cd/m^2
 
Section 7.2: Added and to ETDRS LogMAR Visual Acuity study procedure steps and removed
 
Appendix D: Added and to Appendix D
 
Section 10: Updated Table 8. Examples of major and minor protocol deviations to specify timing for visual performance for OD throughout; updated timing allowed for visual performance; corrected typo.
 
Section 14.7: Added contact lens fitting assessment to the exploratory hypotheses.
 
Section 2.3: Added the non- inferiority margin of 0.05 LogMAR to the primary hypothesis text.
 
Section 5.1: Added Table 2 Subjects Assigned to Treatments and listed the two unique sequences.
 
Sections 5.2 and 5.3: Added clarification and details behind the single masked nature of the study. Corrected typo
 
Section 14.2: Streamlined the sample size justification section and added the non-inferiority margin justification.
 
Section 14.5: Specified that the Per Protocol analysis set is the primary population for the primary endpoint analysis. Added the ITT population as a
 
	
 
Change in personnel
 
Section 7.2. Error in calculation from EV to cd/m2
 
Section 7.2. Incorrect listed for ETDRS LogMAR Visual Acuity procedures 
 
Appendix D. Omitted
 
Section 10. Clarified the timing is based on OD drop administration time; increased time ranges allowed; updated from "3-minute" to "10- minute" under the major 10-minute deviation category 
Section 14.7. Contact lens fitting assessment was also part of the study procedures.
 
Section 2.3. For completeness
 
Section 5.1. For better clarity and completeness
 
Sections 5.2 and 5.3. For better clarity and completeness
 
Sections 14.2. For better clarity and completeness
 
Sections 5.2 and 5.3. For better clarity and completeness
 
Sections 14.2. For better clarity and completeness
 
Section 14.5. To align the analysis population to a non-inferiority analysis
 
To assess the robustness of results for the primary endpoint analysis
 
Correction of typos
 
Section 14.9. Correction of a typo as the observed case data was listed as both primary and
 

	24 April 2023

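### Section 14.5 lets the per-protocol set alone decide non-inferiority and gives the planned ITT analysis no role, although per-protocol membership is settled after dosing

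*Combined protocol and SAP*

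**What the plan says.** Section 14.5 names the deciding set: "logMAR visual acuity will be assessed on Per-Protocol (PP) population". Non-inferiority is declared when the upper limit of the two-sided 95% CI for Test minus Control is under 0.05 logMAR, and "The primary hypothesis must be met for the study to be successful". There are no secondary analyses (14.6).

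The ITT analysis is described once, in the same section: "A sensitivity analysis for the primary hypothesis will be performed on intention-to-treat (ITT) population to assess the robustness" of the conclusion. Neither a pass criterion nor a reading of a PP/ITT conflict is given.

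Section 14.3 defines PP as "All subjects who successfully complete the study and do not substantially deviate from the protocol", with a trial cohort review committee deciding before hard lock and documenting its reasons. ITT is every randomised subject.

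The Change History records why PP became primary in version 2.0: "To align the analysis population to a non-inferiority analysis". Section 14.5 adds two supporting remarks. Major deviations should be very few in a single-visit study, and "The sample size was calculated conservatively in both the treatment effect size and assumed drop-out rate". It then concludes: "Hence, the PP and ITT populations are expected to be similar".

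Section 14.2 plans about 45 subjects "with a target of at least 38 to complete the study, assuming a 15% drop-out rate". Table 1 shows 45 randomised and 38 completing. Section 14.9 says no drop-out is foreseen, bases efficacy analyses on observed cases, and adds multiple imputation as a sensitivity analysis if more than 10% (4 subjects) have missing data.

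**The concern.** PP excludes subjects for things that happen after a drop has been instilled. Three features let those exclusions depend on the drop:

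- Step 1.23 discontinues a subject whose lens fit is unacceptable after Drop #1. The 10-minute reading has already been taken at step 1.22, so the subject has Drop #1 data but is not a completer.
- Table 8 classes a right-eye reading at 6 minutes or less, or at 16 minutes or more, as a major deviation for the 10-minute test. Such a subject can have both 10-minute readings and still leave PP.
- Section 5.2 leaves the staff who collect the data unmasked, and nothing says that the cohort review committee is masked.

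Exclusions after dosing can move the Test minus Control difference either way. If those removed saw worse with the test drop, the error favours non-inferiority. The analysis that could reveal this is already planned, but the written decision rule does not use it. The claim at stake supports EU registration.

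**Working it through.** **Inputs from section 14.2.** Within-eye variances 0.005117 and 0.005213; covariance 0.003170; subject intercept 0.003322; assumed true difference 0.025; margin 0.05; 38 completers. Both eyes are measured (section 7.2).

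**1. The plan's power.**
- Variance of the within-eye difference = 0.005117 + 0.005213 − 2 × 0.003170 = 0.00399.
- Averaging two eyes, taken as independent as in the stated matrix: 0.00399 / 2 = 0.001995 per subject.
- SE at 38 subjects = √(0.001995 / 38) = 0.00725.
- Noncentrality = (0.05 − 0.025) / 0.00725 = 3.45.
- Power from the noncentral t with 36 or 37 df = 91.9%, against 91% in Table 10. The plan's figure reproduces.
- Enrolment: 38 / (1 − 0.15) = 44.7, rounded up to 45. This also reproduces.

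**2. Does the allowance fit the other sections?** 45 − 38 = 7, and 7 / 45 = 15.6%. That is above the 10% trigger in section 14.9, which foresees no drop-out.

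**3. Cost and benefit of requiring both sets.** Simulation with 40,000 replicates. Subject mean differences are normal with variance 0.001995. Upper bounds use the estimated variance and t with n − 2 df. ITT is all 45 and PP is 45 − k, with a true PP difference of 0.025. The k excluded subjects are taken to have both 10-minute readings. Their mean difference is my assumption, as the documents give none.

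| Excluded (k) | Assumed mean in excluded | PP passes | ITT passes |
|---|---|---|---|
| 7 | 0.025 (same as the rest) | 92% | 96% |
| 2 | 0.10 | 95% | 87% |
| 4 | 0.10 | 94% | 70% |
| 7 | 0.10 | 92% | 37% |

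In the first row both sets pass in 91.3% of trials, against about 92.0% for PP alone. The loss is 0.6 to 0.7 points across repeat runs. With 7 excluded and milder means, PP passes while ITT fails in about 6–7% of trials (mean 0.05) or 21–26% (mean 0.075). The lower end of each range treats the variance as known.

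**4. Excluded subjects with period 1 only.** Generalised least squares with the plan's covariance matrix and subject intercept, and drop, sequence and period as fixed effects. The data are 38 completers at 0.025 plus 7 subjects with period 1 only. Those given the test drop first are assumed to read a further 0.075 worse.
- 4 of the 7 test-first: ITT estimate about 0.026, a shift of about 0.001; ITT passes about 90%.
- All 7 test-first: shift of about 0.002; ITT passes about 88%.
- PP passes about 92% in either case.

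A randomised subject with no 10-minute reading adds nothing to an observed-case ITT analysis.

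**The case against.** PP as primary with ITT for robustness is a coherent approach to non-inferiority, and the plan records that reason. A reader might infer that PP was chosen because it was expected to match ITT. The Change History does not support that: similarity is a supporting remark, and its other leg, few major deviations in one visit, is reasonable.

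A reader might also take 45 to 38 as forecast attrition among randomised subjects. The documents do not support that either. Section 14.5 calls the allowance conservative, 14.9 foresees no drop-out, and discontinued subjects may be replaced. Section 4.3 counts a subject as enrolled at consent, so some of the 7 could be screen failures, who belong to neither set; only Table 1 puts 45 at randomisation. What stands is an inconsistency between sections.

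The largest contrasts are the easiest to over-read. The 92% against 37% result needs 7 excluded subjects who all have both readings and average twice the margin. A still more extreme case sets the mean over all 45 at exactly 0.05 with 7 excluded averaging 0.10, so the PP mean is (45 × 0.05 − 7 × 0.10) / 38 = 0.0408. The PP-only rule then declares non-inferiority about 23% of the time, against 1.5% when both sets must pass. No figure in the plan supports either scenario, and the historical means in Table 9 are equal (0.09 and 0.09). A drop-out will nearly always lack period 2, because only lens fit, lens removal and the exit examination follow the last reading. Subjects with both readings leave PP mainly through major deviations; the examples given are clock-time windows with no evident link to vision.

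Finally, that ITT cannot alter the conclusion is inferred from silence. The separate SAP promised in 14.1 could state how a conflict is read, and committee decisions are documented before lock. None of this puts a rule into the text as it stands.

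**Conclusion.** The point holds as a gap in the decision rule. Under section 14.5, PP success with ITT failure is a success, and conservative sizing is no reason to expect the sets to be alike. It is not shown that PP was chosen for the wrong reason, that 7 subjects will be lost, or that the result will be biased.

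The size depends on who is excluded. With 2 to 4 excluded subjects who have both readings and an assumed mean difference of 0.10, ITT passes 8 to 24 points less often than PP. With period 1 data only, the gap is about 2 to 4 points. If excluded subjects resemble the rest, requiring both sets leaves power at about 91%, above the stated 90% minimum. These figures use the plan's variance, independent eye differences and a true PP difference of 0.025. The change is cheap and worth making, since it costs almost nothing if the sets match as the sponsor expects.

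**What to change.** - Keep PP as the primary set. Change the success rule in 14.5, and the SAP to match, so that non-inferiority is declared only if the upper bound of the two-sided 95% CI is below 0.05 logMAR in both the PP and the ITT set, using the same mixed model on observed data.
- State how the ITT analysis treats subjects with one 10-minute period or none.
- Delete the inference from conservative sizing to similar sets.
- Reconcile 14.2, 14.5 and 14.9 on expected drop-out, and say whether 45 counts consented or randomised subjects.

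Both analyses are already planned, so no data or visits are added. The cost is a few sentences and the 0.6 to 0.7 points of power shown above. Because the protection is small for subjects with period 1 only, the new rule does not replace the multiple-imputation sensitivity analysis in 14.9.

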1.10	Remove Habitual Contact Lenses	Remove habitual contact lenses and store in a case with non-preserved saline.	
1.11	Slit Lamp Biomicroscopy	The FDA slit lamp classification scale will be used to grade the findings and determine eligibility. If there are any Grade 3 or higher other slit-lamp findings, the subject is ineligible to continue at this time, but may return up to one additional time to determine eligibility. If discontinued a final examination must be completed. If there are no slit lamp findings, and the clearance of the fluorescein needs to be expedited, preservative- free saline may be instilled.	

	Visit 1: Baseline			
Step	Procedure	Details		
1.12	Expanded Sodium Fluorescein Corneal Staining	Corneal Staining Assessment (FDA grading scale) will be assessed using a more detailed scale for internal purposes only.		
1.13	Eligibility After Baseline	All responses to Inclusion Criteria questions must be answered "yes" and all responses to Exclusion Criteria questions must be answered "no" for the subject to be considered eligible.		
1.14	Re-insert Habitual Lenses	Habitual Lenses will be re-inserted.		
1.15	Settling Time	Allow habitual lenses 5 minutes to settle.		
1.16	Baseline Distance ETDRS LogMAR Visual Acuity	
 
Under high illumination and high chart luminance, record the distance (4 meter) ETDRS low contrast visual acuity OD (LC1) and OS (LC2). Note:
 
The room illuminance must be between 7.3 and 7.9 EV (394-597 lux).
 
Distance Low Contrast chart luminance acceptable range between 10.5 -10.7 EV (181-208cd/m^2)
 
		

	Visit 1: Treatment 1			
Step	Procedure	Details		
1.17	Randomization and Drop Selection	Assign the first study drop (Drop#1) based on the randomization schedule.		
1.18	Drop Instillation	The investigator will break the seal of drop #1 and discard the first drop. The investigator or technician will instill 1 drop in the right eye. Wait 1 minute and then instill 1 drop in the left eye.		
1.19	Subject Reported Ocular Symptoms	Subjects will respond to a verbal open-ended symptoms questionnaire.		
1.20	Drop Settling	Allow the drops to settle for 3 minutes (from OD drop #1 administration).		
1.21	3-minute Distance ETDRS LogMAR Visual Acuity (From OD Drop #1 Administration Time)	Under high illumination and high chart luminance, record the distance (4 meter) ETDRS low contrast visual acuity OD (LC3) and OS (LC4).		

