1.22	10-minute Distance ETDRS LogMAR Visual Acuity (From OD Drop #1 Administration Time)	Under high illumination and high chart luminance, record the distance (4 meter) ETDRS low contrast visual acuity OD (LC1) and OS (LC2).		

	Visit 1: Treatment 1			
Step	Procedure	Details		
1.23	Habitual Contact Lens Fit Assessment Following the Application of Drop #1	
 
Evaluate and grade lens centration, primary gaze movement, up-gaze movement, and tightness (push-up test).
 
The subject should not proceed to wear the lenses if any of the following is observed: 
 
presence of limbal exposure (appearance of clear cornea) in any gaze
 
presence of edge lift
 
presence of unacceptable movement (excessive or insufficient) in all three movement categories (primary gaze, up-gaze, and push-up)
 
 
 
NOTE: If lens fit is unacceptable subject will be discontinued from the study.
 
		
1.24	Washout	Allow at least 90 minutes before continuing to the second drop as per the randomization schedule. (Subject will continue to wear their habitual lenses during this period.)		

	Visit 1: Treatment 2			
Step	tep Procedure Details			
1.25	Drop Instillation	The investigator will break the seal of Drop #2 and discard the first drop. The investigator or technician will instill 1 drop in the right eye. Wait 1 minute and then instill 1 drop in the left eye.		
1.26	Subject Reported Ocular Symptoms	Subjects will respond to a verbal open-ended symptoms questionnaire.		
1.27	Drop Settling	Allow the drops to settle for 3 minutes (from OD drop #2 administration).		
1.28	3-minute Distance ETDRS LogMAR Visual Acuity (From OD Drop #2 Administration Time)	Under high illumination and high chart luminance, record the distance (4 meter) ETDRS low contrast visual acuity OD (LC3) and OS (LC4).		
1.29	10-minute Distance ETDRS LogMAR Visual Acuity (From OD Drop #2 Administration Time)	Under high illumination and high chart luminance, record the distance (4 meter) ETDRS low contrast visual acuity OD (LC1) and OS (LC2).		

	Visit 1: Treatment 2			
Step	Procedure	Details		
1.30	Habitual Contact Lens Fit Assessment Following the Application of Drop #2	Evaluate and grade lens centration, primary gaze movement, up-gaze movement, and tightness (push-up test).		
		The subject should not proceed to wear the lenses if any of the following is observed:		

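### The primary model and the power calculation set the correlation between a subject's two eyes' Test-minus-Control differences to zero; if it is positive, the confidence interval is too narrow and one-sided error exceeds 2.5%

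*Combined protocol and SAP*

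**What the plan says.** Section 14.5 fits a linear mixed model to the 10-minute monocular readings, with fixed effects for drop, sequence and period. The only random effects are site and subject. The residual part is confined to one eye: "The covariance of residuals between measurements on the same eye across periods within the same subject (R-side) will be modeled using Unstructured (UN) covariance structure". Compound symmetry is named as a fallback if the model does not converge, and Kenward-Roger supplies the denominator degrees of freedom.

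Section 14.2 uses the same structure for the sample size: "An unstructured (UN) covariance matrix was used to model the residual errors between measurements within the same subject and eye across study periods". Its variance inputs are "Subject intercept: 0.003322" and one 2x2 matrix with diagonal 0.005117 and 0.005213 and off-diagonal 0.003170. On the effect, "it was assumed that the visual performance of the investigational eye drop is 0.025 logMAR lower compared to the control eye drop". Table 10 gives 91% power with 38 subjects, a number chosen "in order to achieve a statistical power of at least 90% for the primary endpoint".

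Under Section 7.2 (steps 1.18 and 1.25) the right eye is dosed first, then: "Wait 1 minute and then instill 1 drop in the left eye". Both eyes are read at the 10-minute assessment in each period (steps 1.22 and 1.29).

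**The concern.** The two eyes of a subject are tied together only by an intercept that is the same in both periods. The model therefore gives a right-eye and a left-eye reading the same covariance whether they come from the same period or from different ones. Anything that both eyes share within one period has nowhere to go: the subject's own response to that drop, or the subject's state in that part of the visit. The fixed period effect removes only the average shift between periods. Kenward-Roger adjusts degrees of freedom and small-sample standard errors within the stated covariance; it cannot supply a missing term.

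The study succeeds or fails on one comparison, the upper limit of the two-sided 95% interval against 0.05 logMAR. If the shared part is positive, that limit is too low, and a drop that is truly 0.05 worse passes more often than 2.5% of the time. The error favours the sponsor's claim in a confirmatory study meant to support EU registration.

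**Working it through.** **Inputs.** From Section 14.2: subject variance 0.003322; per-eye matrix 0.005117, 0.005213, covariance 0.003170; assumed difference 0.025; margin 0.05; two-sided alpha 0.05; 38 completers. From Section 7.2: two eyes per subject. Assumed: 19 subjects per sequence, since the allocation ratio is not stated, and rho = 0.1, 0.3 and 0.5, since the documents give no value.

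**What the model implies.** Let c be the covariance of any right-eye reading with any left-eye reading of one subject. It is the same within and between periods, so

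Cov(D_OD, D_OS) = c + c − c − c = 0.

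The site effect cancels in the same way.

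**Reproducing Table 10.**
- Variance of one eye's difference: v = 0.005117 + 0.005213 − 2(0.003170) = 0.00399 (SD 0.063).
- With 76 independent differences: SE = √(0.00399/76) = 0.00725.
- Noncentrality = (0.05 − 0.025)/0.00725 = 3.45.
- Power = 91.9% with 36 df, or 92.6% with 74 df; the plan states 91%.
- Counting one independent difference per subject (equivalent to rho = 1) gives 66% to 68%.

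The stated figure is therefore close to what independent eyes give.

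**Allowing a correlation.** The true SE is √(v(1 + rho)/76), while the planned model still estimates √(v/76). The large-sample one-sided error is 1 − Φ(1.96/√(1 + rho)). With v held at 0.00399, the shared subject-by-period SD that produces a given rho is √(rho·v/2). Valid power uses the correct SE and 36 df.

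| rho | Shared SD (logMAR) | One-sided error, planned test | Valid power, 38 completers | Completers for 90% |
|---|---|---|---|---|
| 0 | 0 | 2.5% | 91.9% | 36 |
| 0.1 | 0.014 | 3.1% | 89.3% | 39 |
| 0.3 | 0.024 | 4.3% | 83.8% | 46 |
| 0.5 | 0.032 | 5.5% | 78.3% | 53 |

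Valid power falls below 90% once rho exceeds about 0.07.

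**Simulation of the planned model.** REML fits of the planned covariance (subject intercept plus per-eye unstructured matrix, 74 df in place of Kenward-Roger, no site term or covariates) gave errors of 3.0%, 4.2% and 5.8% at rho 0.1, 0.3 and 0.5 in 12,000 replicates. A separate run of 3,000 replicates gave 3.9% at 0.3 and 4.8% at 0.5 (Monte Carlo SE about 0.3 points). In that run the estimated v stayed near 0.0039 to 0.0040 whatever rho was, so the SE does not adapt. In the larger run, the model with a subject-by-period term gave 2.2%, 2.4% and 2.5%, and the two-eye mean 2.4%, 2.4% and 2.5%.

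**Power of the planned test.** A period-adjusted eye-level simulation gave 91.5%, 89.9% and 88.4% at a true difference of 0.025, but at the inflated error rates above.

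**The case against.** - **Rho is unknown.** The range 0.1 to 0.5 is an assumption. The two eyes are read separately on different charts, and the left eye is dosed a minute later, which favours eye-specific noise. This stands: the size of the inflation cannot be settled from the documents. It is also a reason to let the model estimate the shared part.
- **A separate SAP is announced.** Section 14.1 calls the protocol text a general description, so a suitable term could still be added. That is true, but the text supplied names the random effects and the residual block explicitly and does not include one.
- **The verdict would rarely change.** With the planning variance, the planned test passes if the estimate is below about 0.0356; at rho 0.5 a valid test needs it below about 0.0320. The chance of falling between the two is about 0.01% at a true difference of 0 (both historical means in Table 9 are 0.09), 0.5% at 0.01, 5% at 0.02 and 10% at 0.025. This limits the practical impact. It does not restore the error rate at a true difference of 0.05, which is what the test has to control.
- **Up to 45 will be randomised.** Section 14.9 expects no dropout. If all 45 complete, valid power at 0.025 is about 93.8%, 89.6% and 85.0% at rho 0.1, 0.3 and 0.5. This softens the power point and leaves the type I error untouched.
- **The 91% is not an arithmetic error.** Agreed. It rests on an unstated zero correlation.

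**Conclusion.** The concern holds, as a conditional statement. That the planned covariance sets the correlation of the two eyes' differences to zero follows by algebra from Sections 14.2 and 14.5, and Table 10 is approximately reproduced on that basis. If the correlation is positive, the non-inferiority interval is too narrow and the one-sided error is above 2.5%: roughly 3% at rho 0.1, 4% at 0.3 and 5% to 6% at 0.5. Table 10's 91% is then not the power of a test that holds its error rate.

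A positive value is plausible from the design but is not documented. At rho 0 nothing is lost; at a negative rho the interval is too wide. The deliberately cautious 0.025 protects power: at rho 0.5 valid power with 38 completers is 91% at a true difference of 0.02, 99% at 0.01 and above 99.9% at 0. It does not protect the type I error. This should be fixed before database lock.

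**What to change.** In Section 14.5, and in the SAP, add a random subject-by-period effect to the planned model. Either of two alternatives also works:
- analyse the two-eye mean per subject and period; or
- replace the subject intercept and the per-eye block with a 4x4 unstructured matrix over eye and period within subject. This is more general, at 10 parameters, and is not equivalent to the first option.

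In Section 14.2, estimate rho from the historical crossover behind Table 9 (62 eyes per drop) and restate the power at 38 completers for that value, even if it falls below 90%. State also the true difference at which 90% still holds: 0.0247, 0.0225 and 0.0204 at rho 0.1, 0.3 and 0.5. If 90% at 0.025 is to be kept, the completer numbers in the table above apply.

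The cost is one model term and a restated power figure. The interval widens by √(1 + rho), about 5%, 14% and 22% at rho 0.1, 0.3 and 0.5. At rho 0, power with the added term was 91.7% in 4,000 replicates, so almost nothing is lost. Keeping 90% at 0.025 could require more than 38 completers.
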